1. INTRODUCTION

This plan describes a planned statistical analysis for the clinical study protocol number KSL0117 of “Dompé farmaceutici s.p.a.”: «A multicenter, double blind, randomized, parallel groups study to assess the efficacy and tolerability after single oral administration of Ketoprofen lysine salt 40 mg granules versus Placebo in male and female subjects with acute pain syndrome after removal of molar teeth».

2. LIST OF ABBREVIATIONS

Abbreviation	Explanation
AA	Arachidonic acid
ADME	Absorption, Distribution, Metabolism, Excretion
ADR	Adverse drug reaction
AE	Adverse events
ALAT	Alanine aminotransferase
ALT	Alanine transaminase
AR	Adverse Reaction
ASA	Acetylsalicylic acid
ASAT	Aspartate aminotransferase
AUC	Area under the concentration-time curve
BAA	Biologically Active Additives
BAS	Biologically Active Supplements
BMI	Body mass index
BP	Blood pressure
CFS	Cell-free supernatant
CI	Confidence Interval
CNS	Central nervous system
COX	Cyclo-oxygenase
CPR	Creatine phosphokinase
CRF	Case report form
CVS	Cardiovascular system
DNA	Deoxyribonucleic acid
ECG	Electrocardiogram/electrocardiography
eCRF	Electronic Case Report Form
ED	Early discontinuation (early discontinuation visit)
ET	End of treatment
ETV	Early Termination Visit
EU	European Union
FS	Food Supplement
FVC	Forced vital capacity
GI tract	Gastro-intestinal tract
GLP	Good Laboratory Practice
H	Hour
HR	Heart rate
I.V.	Intravenous
IASP	International Association for the Study of Pain
ICD	International Classification of Disease

Abbreviation	Explanation
ICSRs	Individual case safety report
IEC	Independent Ethics Committee (local)
IMP	Investigational medicinal product
ITT	Intention-to-treat population
KA	Ketoprofen acid
KLS	Ketoprofen lysine salt
KP	Ketoprofen
LME	Liner mixed-effect model
LOCF	Last Observation Carried Forward
MedDRA	Medical Dictionary for Regulatory Activities
MoH	Ministry of Health
NSAIDs	Non-steroid anti-inflammatory drugs
NZW	New Zealand White
OA	Osteoarthritis
OTC	Over-the-Counter
PD	Pharmacodynamic(s)
PG	Prostaglandins
PID	Pain intensity different
PK	Pharmacokinetic(s)
POM	Prescription only medications
PP	Population per protocol
PT	Preferred Term
RA	Rheumatoid arthritis
REMD	Rescue medication
RR	Respiration Rate
SADR	Serious adverse drug reaction
SAE	Serious adverse event
SAP	Statistical analysis plan
SAR	Serious adverse reaction
SD	Standard deviation
SDV	Source Data Verification
SmPC	Summary of Product Characteristics
SOC	System Organ Class
SOP	Standard Operation Procedures
TC	Telephone contact
TEAEs	Treatment-Emergent Adverse Events
TESS	Treatment Emergency Signs and Symptoms
TFPR	Time to first perceptible relief
TK	Toxicokinetic
TMPR	Time to meaningful pain relief
ULN	Upper limit of normal
VAS	Visual Analogue Scale
WHO	World Health Organization

3. STUDY DESIGN

This is a multicenter, double-blind, randomized, parallel groups, placebo-controlled study to assess the efficacy and safety of OKITASK® 40 mg granules in patients with acute pain syndrome after removal of molar teeth. The study will be conducted at 3-6 Russian sites. A total expected number of enrolled subjects is 70 (35 per each group). Patients' enrollment to the sites is competitive.

The study will consist of three periods: screening, study treatment and follow-up.

3.1 SCREENING

At Screening after signing the informed consent form, patient's demography, medical history and concomitant medications will be collected, oral cavity will be examined, weight and vital signs will be measured and pregnancy test will be performed for inclusion/exclusion criteria assessment. Screening procedures might take up to 4 days before the scheduled tooth extraction procedure including the actual day of extraction.

On Day 1 the patient will undergo extraction of a molar tooth as indicated for the patient's dental condition. The tooth extraction will be conducted using routine technics and anesthetics (recommended types of anesthesia are provided in section 5.9 Concomitant and rescue therapy of the protocol). After that the patient will stay at the site for treatment of pain syndrome according to the protocol.

Pain intensity will be assessed using VAS within 3 hours after the tooth extraction procedure. Patient's overall assessment will be also recorded. If pain intensity on VAS is above 30 mm and pain relief is required, the patient will be randomized in the study.

3.2 STUDY TREATMENT

The patients will be assigned to one of two treatment group in 1:1 ratio:

- Group 1. OKITASK® 40 mg – 35 patients
- Group 2. Placebo – 35 patients

The patient will assess pain by VAS at 0' – immediately before study drug dosing.

Upon study drug administration the patients will immediately start two stopwatches. One of them will be stopped once the patient feels first perceptible pain relief; the second one will be stopped once the patient feels the meaningful pain relief.

The patient will stay at the site for 6 hours post-dose for pain and AE assessment. Pain intensity will be assessed by VAS at 5', 10', 15', 30', 45', 60' (1 hour), 90' (1.5 hours), 120' (2 hours), 180' (3 hours), 240' (4 hours), 300' (5 hours), and 360' (6 hours) post-dose.

Pain relief will be assessed by VAS at 5', 10', 15', 30', 45', 60' (1 hour), 90' (1.5 hours), 120' (2 hours), 180' (3 hours), 240' (4 hours), 300' (5 hours), and 360' (6 hours) post-dose.

Patients should mark actual time points of VAS measurement. Deviations from planned time points will not be considered as protocol deviations. Only omitted values will be considered as protocol deviations.

Patients' overall assessment will be performed right before the discharge from the site.

Follow-up phone call to the patient to assess AEs will be performed on Day 3 (48 hours

after the study drug dosing). Any SAE spontaneously reported by the patient within 30 days of dosing will be collected.

Should the patient require rescue medication at any time during 6 hours post-dose, the last VAS measurement and patient's overall assessment will be performed before the rescue medication dosing.

3.3 FOLLOW-UP

Follow-up phone call to the patient to assess AEs will be performed on Day 3±1 (48 hours after the study drug dosing). Any SAE spontaneously reported by the patient within 30 days of dosing will be collected.

The study procedures schedule is summarized in Table 3.1.

Table 3.1 Schedule of visits and procedures

Test/Examination	Screening	Study treatments													ED ¹	Follow-up
		Time (Post-dose)														
Day	Day-4...Day 1	Day 1													Day 1	Day 3±1
		0.08	0.17	0.25	0.5	0.75	1	1.5	2	3	4	5	6	>1	48	
		5	10	15	30	45	60	90	120	180	240	300	360	>60		
Informed consent & screening n° assignment		X														
Demography		X														
Medical history and underlying disease		X														
Oral cavity examination		X														
Height		X														
Weight		X														
Vital signs		X														
Pregnancy test		X														
Extraction of a molar tooth	X (Day 1)															
Pain Intensity Assessment VAS (0-100 mm) ³	X	X														
Inclusion/exclusion criteria ⁴	X															
Randomization number assignment			X													
Patient's overall assessment (5-point scale) ⁵				X											X	X
Pain Relief Assessment VAS (0-100 mm)																
Time to first perceptible relief (TFPR) measured by stopwatch ⁶														X		
Time to meaningful pain relief (TMRP) measured by stopwatch ⁷														X		
Rescue medication (if applicable) ⁸															X ⁹	
Concomitant medications	X	X													X	X
Previous therapy(ies)	X	X														
Adverse events	X	X												X	X	

¹ Should the patient require rescue medication at any time during 6 hours post-dose, the last VAS measurement and patient's overall assessment will be performed before the rescue medication dosing. Subjects will be encouraged to postpone the rescue medication until after 1-hour post-dose. The ED assessments will be performed before rescue treatment; actual time of VAS will be captured.

² After surgery, before the study drug administration

³ Patients should mark actual time points of VAS measurement. Deviations from planned time points will not be considered as protocol deviations. Only omitted values will be considered as protocol deviations.

⁴ Confirmation of the Inclusion/Exclusion criteria prior to randomization

⁵ Patients should mark actual time points of VAS measurement. Deviations from planned time points will not be considered as protocol deviations. Only omitted values will be considered as protocol deviations.

⁶ The time of stopwatch will be recorded on eCRF

⁷ The time of stopwatch will be recorded on eCRF

⁸ Height will be registered as reported by the patient.

⁹ In the event of poor pain control, subjects will be allowed access to rescue medication for analgesia (Paracetamol 500-1000 mg). Time to REMD (rescue) with an alternative analgesic, if it occurred, will be recorded. Subject will be encouraged to postpone the rescue medication until after 1 h post dose. If Paracetamol 500-1000 mg is not effective, the patient will be allowed to take another dose of Paracetamol 500-1000 mg every 6-8 hours; maximum daily dose is 4000 mg.

3.4 RANDOMIZATION AND RECEIVING OF THE STUDY DRUG

This is a double-blind placebo-controlled study. Patients will be assigned to one of two treatment groups by the IWRS system in 1:1 ratio:

- Group 1. OKITASK® 40 mg – 35 patients
- Group 2. Placebo – 35 patients

Randomization will be performed after the surgery upon confirmation of the inclusion/exclusion criteria (VAS ≥ 30 mm). The double-blinding is provided by Placebo that is identical to OKITASK® 40 mg granules.

3.5 BLINDING

The drug will be packaged and labeled in a manner that will exclude unblinding. IWRS will assign the study drug kit number that should be administrated by the subject. Randomization and IWRS manual will be provided to the Investigator before the beginning of the study.

3.6 UNBLINDING

The code of a particular subject may be broken in a medical emergency if knowing the identity of the treatment allocation would influence the treatment of the subject. Administration of rescue therapy does not require code break. Unblinding of a patient's treatment may be performed in IWRS. The reason for breaking the code must be documented in the source documentation. If possible, Medical Monitor should be contacted before the code is broken; otherwise the Medical Monitor should be notified within 24 hours of breaking the code.

4. CONCOMITANT MEDICATION

All concomitant medications, including herbal therapy and biologically active supplements (BAS) must be registered in the source documentation and on the eCRF. This includes all pharmaceutical products and BAS.

The concomitant therapy also includes anesthesia and rescue therapy allowed by the protocol which is applied to relief pain (if applicable).

Ultracain D (articaine 40 mg), Ultracain DS forte (articaine+epinephrine 40 mg+0.01 mg/ml), Ultracain DS (articaine+epinephrine 40 mg+0.005 mg/ml) 1-2 capsules can be used for anesthesia. The Investigator can choose anesthesia taking into consideration the patient's condition, medical history and other reasons. Number of used capsules and type of anesthesia for each patient will be recorded in the source documentation and on the eCRF.

In the event of poor pain control, the patient will receive a rescue medication for analgesia (i.e. Paracetamol 500-1000 mg tablets). Subjects will be encouraged to postpone the rescue medication until after 1-hour post-dose. If Paracetamol 500-1000 mg is not effective, the patient will be allowed to take another dose of Paracetamol 500-1000 mg every 6-8 hours; interval between dose taking is not less than 4 hours; the maximum daily dose is 4000 mg.

The drug name (preferably the name of the active substance), dosage, frequency of administration, route of administration, indication for use (including the underlying disease, comorbid conditions, adverse event, or prevention), the date of beginning and ending of a concomitant drug administration should be registered in the source

documentation and on the electronic Case Report Form.

If by the time of the study completion the concomitant therapy continues, a corresponding mark shall be entered on the electronic Case Report Form.

4.1 PROHIBITED THERAPY

Prohibited medicines which should not be taken within 48 hours before screening and during Day 1:

- Antihistamines;
- Sedating medication (including herbal therapy and BAS).

Prohibited drugs should not be taken during Day 1:

- Medicines for anesthesia other than indicated by the protocol (e.g. procaine, lidocaine);
- NSAIDs and combinations which contain NSAIDs (except for the study drug);
- Analgesics: opioids, acetylsalicylic acid and its derivate, pyrazolones, other analgesics-antipyretics (except for the rescue therapy indicated by the protocol, if applicable);
- Antithrombotic medicines;
- Hemostatic sponge.

Participation in the evaluation of any investigational product within 3 months before screening and during the study is also prohibited.

5. OBJECTIVES OF CLINICAL STUDY

5.1 PRIMARY OBJECTIVES

The primary objective of this study is to assess the efficacy of OKITASK® 40 mg granules versus Placebo in patients with acute pain syndrome after removal of one molar tooth by comparing AUC_{0-6h} of post-treatment pain profile measured by VAS.

5.2 SECONDARY OBJECTIVES

Secondary objectives of this study are to assess the following efficacy and safety parameters of OKITASK® 40 mg granules versus Placebo in patients with acute pain syndrome after removal of one molar tooth:

- Time profile of pain and time profile of pain relief using VAS scales
- Time to first perceptible pain relief (TFPR) and time to meaningful pain relief (TMPR)
- Proportion of patients requiring rescue medication and time to rescue medication
- Patient's overall assessment
- Rate of adverse events (AE)

6. DETERMINATION OF SAMPLE SIZE¹

Sample size calculation was based on the paper of Seymour 1996 [3] concerning a randomized, double-blind, placebo-controlled study of treatment with placebo, paracetamol (500 and 1000 mg) and ketoprofen (12.5 and 25 mg).

The unadjusted AUC_{0-6h} values for placebo and ketoprofen were about 263 and 173 mmh⁻¹, respectively. The corresponding SD were 106 mm h⁻¹ (about 40% of the mean value for placebo AUC) and 121 mmh⁻¹ (about 70% of the mean value for ketoprofen 25 mg AUC).

The testing hypothesis for this trial is the superiority of ketoprofen versus placebo that in statistical term is:

H_0 : mean of placebo \geq mean of ketoprofen (no difference between treatments)

H_1 : mean of placebo $<$ mean of ketoprofen (clinically and statistically significant difference between the groups) $\Delta=90$ mm h⁻¹

A total of 58 subjects (29 subjects per group) will be necessary to assess a difference of 90 mm h⁻¹ between the groups with a power of 80%, $\alpha = 0.05$, SD=121 mmh⁻¹, and randomization rate of 1:1. Sample size calculation was performed using SAS 9.2².

Assuming a drop-out rate of 15%, 70 subjects in total (35 subjects per group) should be enrolled. Considering the screen-failure rate of about 30%, up to 100 patients will be screened in the study.

7. REPLACEMENT OF THE MISSING DATA

7.1 PRIMARY EFFICACY

Considering that the primary variable AUC_{0-6h} is derived from pain intensity VAS measurements, analyses on primary and secondary variables without or with substitution of missing data, using the last observation carry forward (LOCF) methodology, has been considered in order to avoid bias in the inferential testing of treatment effect.

For LOCF analysis substitution of missing data will be applied only on all patients that have at least one VAS value post-baseline (patient compliant with ITT population definition). Missing post-baseline pain score will be replaced with previous one. **Baseline data (pre-dose) could be carried forward also.** Possibility to use baseline data comes from the data nature, which seems to be linearly decreasing over time. This will allow to calculate AUC in case of missing first post-baseline value (5 minutes).

If data be missing more than one time point after baseline, the data will be qualified as invalid. Consecutive missing values will be replaced with the last non-missing (observed) value. If more than two time points data are missing and after missing data some points have values (non-missing), then all missing sequence will be replaced with last non-missing value. In case of absence non-missing values after two missings, no replacement will be done and data will be find invalid for analysis. Possible cases are presented in table below:

¹ Cite from the Study Protocol

² SAS 9.2 <http://support.sas.com/documentation/92/>

Table 7.1 LOCF missing data replacement cases

Time points	Scale	Scale LOCF	AUC
0 (baseline)	A	A	Valid
1	B	B	
2	.	B	
3	.	B	
4	C	C	
5	D	D	
0 (baseline)	A	A	Valid
1	.	A	
2	B	B	
3	C	C	
4	D	D	
5	E	E	
0 (baseline)	A	A	Invalid
1	.	.	
2	.	.	
3	B	B	
4	C	C	
5	D	D	
0 (baseline)	A	A	Valid
1	B	B	
2	.	B	
3	.	B	
4	.	B	
5	C	C	
0 (baseline)	A	A	Invalid
1	B	B	
2	C	C	
3	.	.	
4	.	.	
5	.	.	

For the sensitivity analysis the fully conditional specification (FCS) regression method¹ will be used for replacing missing data.

SAS code example:

```
proc mi data=pain round=1. seed=139592 out=pain_imp;
  class trt;
```

¹ Van Buuren 2007; Brand 1999; Rubin 1987

http://documentation.sas.com/?docsetId=statug&docsetTarget=statug_mi_details07.htm&docsetVersion=14.3&locale=en

² Could be any other

```

fcs nbiter=20 reg (pain=time trt time*trt/details);
var pain time trt;
run;

```

Pain dataset description:

Alphabetic List of Variables and Attributes						
#	Variable	Type	Len	Format	Informat	Label
4	pain	Num	8	BEST12.	BEST32.	Pain Intensity (VAS)
1	patid	Num	8	BEST12.	BEST32.	Patient ID
5	site	Num	8	BEST12.	BEST32.	Study site
2	time	Num	8	BEST12.	BEST32.	Time (hours)
3	trt	Char	9	\$9.	\$9.	Therapy

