8.1 INTENT-TO-TREAT POPULATION

The Intent-to-treat (ITT) population will include all randomized patients who receive at

least one dose of study medication and have at least one post-baseline¹ efficacy measurement; it will be based on the treatment randomized, regardless of the treatment actually received. The ITT will be used for all efficacy analyses. Subject will be summarized according to the treatment to which they were randomized.

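### Section 7.1 contradicts itself on gaps followed by an observed reading: it drops patients missing only 5' and 10', and fills interior gaps of any length by LOCF

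*SAP*

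**What the plan says.** Section 7.1 governs missing VAS readings for the primary AUC0-6h, and Section 10.1 refers to it. It makes these statements:

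- Pre-dose values may be used: "Baseline data (pre-dose) could be carried forward also". The reason given is the nature of the data, "which seems to be linearly decreasing over time". The stated purpose is to allow an AUC when the 5-minute reading is missing.
- An exclusion: "If data be missing more than one time point after baseline, the data will be qualified as invalid".
- A replacement rule: "Consecutive missing values will be replaced with the last non-missing (observed) value".
- For more than two missing points with later values present, "then all missing sequence will be replaced with last non-missing value". No limit is set on the length of the gap.
- For a gap that runs to the end: "In case of absence non-missing values after two missings, no replacement will be done and data will be find invalid for analysis".

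Table 7.1 ("LOCF missing data replacement cases") gives five worked cases. Points 2-3 missing is Valid (case 1), point 1 missing is Valid (case 2), points 1-2 missing is Invalid (case 3), points 2-4 missing is Valid (case 4), and points 3-5 missing to the end is Invalid (case 5).

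Section 8.1 admits to the ITT population any randomized, dosed patient with at least one post-baseline efficacy measurement, and adds: "The ITT will be used for all efficacy analyses". Section 10.1 calculates the AUC by the trapezoidal rule on actual times.

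**The concern.** The exclusion sentence and the replacement sentences cannot all be applied as written. Two programmers could therefore differ on who enters the primary analysis.

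The reading that agrees with the table also fits poorly with the information lost. A patient with a baseline and every reading from 15' to 360' is removed from the AUC analysis, while a patient with no reading for several hours is kept with a flat value across the gap.

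At stake are the membership of the ITT primary analysis in a trial of 70, where each patient is 1/35 = 2.9% of an arm, and the accuracy of the AUC for patients with long interior gaps.

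**Working it through.** **1. The plan's scale.** Section 6 gives a difference of 90 mm·h, SD 121, 80% power and alpha 0.05. The normal approximation, two-sided, is n = 2 × (1.960 + 0.842)² × 121² / 90² = 28.4, so 29 per group and 58 in total, as stated. With 15% drop-out, 58/0.85 = 68.2, so 69, or 70 for equal arms. These figures serve only to scale what follows.

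**2. The rules side by side**, for gaps that end in an observed value:

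| Missing readings | Exclusion sentence, literal | Exclusion sentence, as directly after baseline | Replacement sentences with baseline carry-forward | Table 7.1 |
|---|---|---|---|---|
| First only | kept | kept | filled | Valid (case 2) |
| First two | Invalid | Invalid | filled | Invalid (case 3) |
| First three or more | Invalid | Invalid | filled | no case |
| Two interior | Invalid | kept | filled | Valid (case 1) |
| Three interior | Invalid | kept | filled | Valid (case 4) |

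The literal reading fails on cases 1 and 4. The narrower reading agrees with every worked case but collides with the replacement sentences for three or more missing first readings, and the table does not settle that.

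**3. What case 3 discards.** On the Section 3.2 schedule, points 1 and 2 are 5' and 10'. Suppose both true values lie 10 mm off the straight line from baseline to 15' (an assumption). Each reading has a trapezoid weight of 5 min, so the error from bridging is 10 × (5 + 5)/60 = 1.67 mm·h, or 1.4% of the SD of 121.

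**4. What an interior gap adds under LOCF.** Let 3, 4 and 5 h be missing and 2 and 6 h observed, with pain falling at d mm/h. The carried 2 h value is too high by d, 2d and 3d, each with a weight of 1 h, so the AUC is overstated by 6d:

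- d = 3: 18 mm·h
- d = 5: 30 mm·h
- d = 8: 48 mm·h

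These are errors in one patient's AUC. In the mean of a 35-patient arm they are 18/35 = 0.5, 30/35 = 0.9 and 48/35 = 1.4 mm·h per affected patient, or 0.6% to 1.5% of 90. The trapezoid between the 2 h and 6 h values has no error on a straight line.

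**5. Direction between arms.** Take straight lines through the planning AUCs (173 ketoprofen, 263 placebo) from an assumed baseline of 50 mm. The 6 h values are 173/3 − 50 = 7.7 and 263/3 − 50 = 37.7 mm, so the declines are 7.06 and 2.06 mm/h. The same gap adds 42.3 mm·h in a ketoprofen patient and 12.3 in a placebo patient. For assumed baselines of 40 to 55 mm the ranges are 22.3 to 52.3 and −7.7 to 22.3. The placebo value is negative at 40 mm because an AUC of 263 then implies rising pain.

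For a longer gap, 120' to 300', the additions at 50 mm are 55.6 and 16.2. If 10% of each arm had it, the treatment difference would shrink by 0.1 × (55.6 − 16.2) = 3.9 mm·h, about 4% of 90.

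**6. Where pain returns.** On an assumed curve from 50 mm to 20 mm at 2 h and then up to 45 mm at 6 h, LOCF over 3 to 5 h gives 6 × (−6.25) = −37.5 mm·h, a downward error.

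**The case against.** The exclusion sentence directly follows the remark about a missing 5-minute reading, so a careful programmer would take it to mean directly after baseline and would get all five worked cases right. That stands. It narrows the ambiguity to three or more missing first readings, but does not explain why case 3 should be Invalid.

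A reader might set the 18 to 48 mm·h against the planned 90 and infer that LOCF threatens the primary result. The documents do not support this: the first are single-patient errors, the second a difference in arm means. A reader might also infer an upward bias in general, or one that favours the drug. The sign depends on the course of pain. Where pain falls faster on ketoprofen, the bias works against the drug.

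Patients stay at the site for 6 hours, and omitted VAS values count as protocol deviations (Section 3.2), so long interior gaps followed by a reading are probably few. The plan also has an FCS sensitivity analysis and a per-protocol analysis on complete data. These limit the harm but do not settle who belongs in the ITT primary analysis.

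The phrase about linear decline is hedged and is offered only to justify using baseline. Zero interpolation error is therefore a property of the assumed line. If the curve turns inside a long gap, bridging also errs: on the curve in step 6, with 120' to 300' missing, it is off by +21.3 mm·h against −9.4 for LOCF.

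**Conclusion.** The point holds as a drafting contradiction with a modest numerical consequence. It is worth correcting before database lock.

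Two parts need no assumption about pain: the exclusion sentence conflicts with its neighbours and with Table 7.1, and case 3 removes patients whom Section 8.1 places in the ITT population. That the loss in case 3 is trivial (about 1.7 mm·h) rests on the assumed 10 mm deviation.

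The LOCF part is conditional. Where pain falls, as the SAP supposes, the patient's AUC is overstated and the treatment difference tends to shrink. Where pain is flat or rising, the error is nil or downward. The total effect depends on how often such gaps occur, which the SAP does not state.

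**What to change.** For the AUC only:

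- Delete the exclusion sentence from Section 7.1.
- State that any gap followed by an observed value, including one directly after baseline, is bridged by the Section 10.1 trapezoid between the observed neighbours at their actual times, and that the patient stays in the ITT primary analysis.
- In Table 7.1, mark case 3 Valid and show cases 1, 2 and 4 as bridged.
- Change the LOCF label for the primary AUC in Section 10.1 and Table 12.9 (and Table 12.11, which repeats its title) to match.
- Optionally, add a sensitivity analysis without patients who have long interior gaps.

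The rule for gaps that run to the end of the curve, and the LOCF data set for the repeated-measures profile in Section 10.2, are not changed by this point. The cost is minor text and label edits with no new data. The price is reliance on a straight line across any long interior gap, which the optional sensitivity analysis would test.

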8.2 POPULATION PER PROTOCOL

ITT population patients comply with the per-protocol population if they complete the study treatment period, have all assessments for the primary efficacy analysis and considered compliant. The patients are compliant if they do not have any major protocol violations in the course of the study.

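### ITT patients rescued before 3 hours have no primary AUC0-6h, because Section 7.1 of the SAP does not carry forward a run of missing VAS values that lasts to 6 hours

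*SAP*

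**What the plan says.** The primary variable is the area under the pain-intensity VAS from time 0 to 6 hours (Section 10.1). Section 7.1 adopts last observation carried forward (LOCF) "in order to avoid bias in the inferential testing of treatment effect" and gives a general rule: "Consecutive missing values will be replaced with the last non-missing (observed) value". It then makes an exception: "In case of absence non-missing values after two missings, no replacement will be done and data will be find invalid for analysis". The last case of Table 7.1, with three missing values at the end, is marked Invalid.

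Section 3.2 says: "Should the patient require rescue medication at any time during 6 hours post-dose, the last VAS measurement" is taken before the rescue dose. Table 3.1, footnote 1, repeats this and adds that the actual time of that VAS is captured. Table 12.1 lists rescue as a reason for early termination.

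The ITT population needs one dose and one post-baseline efficacy value, and Section 8.1 states: "The ITT will be used for all efficacy analyses". Patients belong to the per-protocol population "if they complete the study treatment period, have all assessments for the primary efficacy analysis and considered compliant" (Section 8.2).

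Section 7.1 also contains a separate sentence: "If data be missing more than one time point after baseline, the data will be qualified as invalid". It comes directly after the rule that lets the baseline value stand in for a missing 5-minute score.

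**The concern.** Early rescue produces exactly the pattern that the exception excludes: observed scores up to rescue and none after it. The patient stays in the ITT population but has no AUC0-6h for the primary LOCF comparison. Selection into the primary test then depends on an event that follows randomisation and reflects the outcome itself. If placebo patients are rescued more often, the placebo arm loses more of its high-pain patients, and the comparison no longer estimates the ITT effect.

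The per-protocol analysis also omits these patients. For the AUC, only the fully conditional specification (FCS) imputation, a sensitivity analysis tabulated beside LOCF in Table 12.9, keeps them. Its example code predicts pain from time, treatment and their interaction, not from the patient's own earlier scores.

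The rule also leaves open which patients are excluded. The text speaks of two missing values and the table shows three, and nothing says whether the pre-rescue VAS fills the next scheduled slot. Two programmers could build different primary datasets.

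**Working it through.** **Step 1. The plan's sample size.** Inputs from Section 6: difference 90, SD 121, α 0.05, power 80%, drop-out 15%. Per arm, n = 2 × (1.960 + 0.842)² × 121² / 90² = 28.4, so 29 (58 in total). With drop-out, 29 / 0.85 = 34.1, so 35 (70 in total). Both figures reproduce with a two-sided test. Noncentral-t power at 35 per arm is 0.866 with SD 121 in both arms, and 0.904 with the SDs of 106 (placebo) and 121 (ketoprofen) that Section 6 also gives.

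**Step 2. Who is excluded.** Section 3.2 schedules the later VAS points at 60, 90, 120, 180, 240, 300 and 360 minutes. The table counts the scheduled points left without a value.

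| Rescue between | Pre-rescue VAS is an extra point | Pre-rescue VAS fills next slot |
|---|---|---|
| 60-90 min | 6 | 5 |
| 90-120 min | 5 | 4 |
| 120-180 min | 4 | 3 |
| 180-240 min | 3 | 2 |
| 240-300 min | 2 | 1 |
| 300-360 min | 1 | 0 |

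The rule may be triggered by two or by three missing values, which gives four readings. Before 3 hours at least three values are always missing, so the AUC is invalid under all four. At 3-4 hours it is invalid under three readings, at 4-5 hours under one, and after 5 hours under none.

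**Step 3. Effect on the difference.** The SAP gives no rescue rate, so the exclusion fractions q and the correlation ρ (0.3 to 0.7) between tendency to rescue and AUC are assumptions. AUC is taken as normal with the Section 6 means of 263 and 173. The mean of retained patients in an arm is μ − ρ × SD × λ(q), with λ(q) = φ(z) / (1 − q) and z the upper-q normal quantile. λ is 0.127, 0.195, 0.274, 0.350 and 0.497 for q = 6%, 10%, 15%, 20% and 30%.

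Example for 30% placebo and 15% active, SD 121 in both arms, ρ = 0.7: 90 − 0.7 × 121 × (0.497 − 0.274) = 71. With ρ = 0.3 the result is 82.

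**Step 4. Power.** These figures come from simulated trials with 35 per arm and a pooled t test, which equals the two-group ANOVA F test. Success means p < 0.05 with the lower mean on active.

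| Excluded, placebo / active | SD 121/121: difference; power | SD 106/121: difference; power |
|---|---|---|
| none | 90; 0.87 | 90; 0.90 |
| 15% / 6% | 78-85; 0.77-0.79 | 80-86; 0.84 |
| 20% / 10% | 77-84; 0.75-0.76 | 81-86; 0.82-0.84 |
| 30% / 15% | 71-82; 0.66-0.70 | 76-84; 0.76-0.77 |

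With equal exclusion of 15% in each arm the difference is 90-93 and power 0.82-0.92 across both SD settings.

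**Step 5. The sentence on values missing after baseline.** Read literally, as any two missing points, it conflicts with Table 7.1 cases 1 and 4, which have two and three missing points inside the profile and are Valid. Read as points missing immediately after baseline, it explains why case 2 (first point missing) is Valid and case 3 (first two missing) is Invalid, and it is compatible with cases 1 and 4.

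**The case against.** The strongest reply is that the size is assumed and modest. No rescue rate is given, and Section 10.2 allows for too few rescues to draw a Kaplan-Meier curve. With SDs of 106/121, power drops below 0.80 only in the heaviest scenario shown. How the study cited in Section 6 scored rescued patients cannot be seen, so the target of 90 is itself an assumption for these patients. This stands, and it limits the stated size. It does not remove the defect, because any patient rescued before 3 hours is lost whatever the rate.

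Carrying the pre-rescue score forward also has a bias, in the drug's favour. This stands too and shapes the fix.

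Three stronger readings are tempting, and the SAP does not support them:

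- A reader might infer that no missing value at the end of the profile is ever filled. A single one still is, under the general rule.
- A reader might infer that rescued patients vanish from all efficacy evidence. Table 7.1 keeps their observed scores and marks only the AUC Invalid, so the repeated-measures model of Section 10.2 may still use those scores. Rescue is also a secondary outcome.
- A reader might call the sentence on values missing after baseline a proven contradiction of Table 7.1. In context it limits baseline carry-forward, so it is ambiguous wording.

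**Conclusion.** The point holds for the primary AUC. Exclusion of patients rescued before 3 hours follows from the SAP's text, table and visit schedule without any assumption, and for rescue at 3 to 5 hours the analysed set is not uniquely defined. This conflicts with the ITT rule of Section 8.1 and with the aim stated in Section 7.1.

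The size is conditional. Under the assumed unequal rates (15%/6% to 30%/15%), the expected difference falls from 90 to about 71-86 mm·h and power to about 0.66-0.84, depending on SD. If the arms lose patients equally at about 15%, the drop-out allowance covers the loss.

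A reader might infer a risk of a false superiority claim. The direction does not support that: losing more high-pain placebo patients shrinks the difference, so the risk is a missed or understated effect.

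**What to change.** Before unblinding:

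1. Remove the exclusion for values missing at the end of the profile and mark the last case of Table 7.1 Valid, so that rescued ITT patients have an AUC0-6h in the primary analysis. Use the pre-rescue VAS at its actual time and state one rule for the remaining time to 6 hours. LOCF to 6 hours is consistent with the plan's own method.
2. Report beside it a multiple imputation that keeps these patients, with one record per patient and with baseline, the patient's own earlier scores and treatment as predictors.
3. Reword the ambiguous sentence to cover two or more consecutive values missing immediately after baseline. Then either justify excluding case 3 or fill it as well. Otherwise a patient missing only the 5- and 10-minute scores is dropped while one rescued at 1 hour is kept.

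The cost is SAP wording and programming, with no extra data or patients.

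The downside of LOCF should be disclosed. Section 7.1 describes pain data as "which seems to be linearly decreasing over time". If a score S at rescue time t is held flat while pain would have fallen linearly to a fraction g of S at 6 hours, the patient's AUC is overstated by S × (6 − t) × (1 − g) / 2. With assumed values this is 50 × 3 × 0.5 / 2 = 37.5 mm·h (rescue at 3 hours, fall to half) up to 70 × 5 × 1 / 2 = 175 mm·h (rescue at 1 hour, fall to zero). With 9 to 15 percentage points more rescue on placebo, the difference is inflated by 0.09 × 37.5 = 3 to 0.15 × 175 = 26 mm·h. If pain would have stayed flat, there is no inflation. If the drug has no effect, both arms share the same rescue pattern and the test keeps its 5% level. The problem is the size of the estimate, which is why the imputation result must stand beside it.

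All of this concerns data handling only, not when rescue is given.
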